2.4 Correlative Objectives

1. Evaluate change in CA 19-9 and other tissue markers before and after treatment and correlate with outcomes.
2. Correlate pathologic tumor response with findings from next generation sequencing (NGS).
3. Outcome and survival data including DFS and OS will be correlated with NGS findings and other future research studies.
4. Any residual tissue and other biologic samples (blood, serum and plasma) will be stored for future research

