10. STUDY CALENDAR

1 cycle = 2 treatments over 28 days (treatments are given every 2 weeks) D1=Day 1 D15=Day 15	Baseline ¹	Cycles 1-2		Surgical Evaluation/EOT ²	Long-term Follow-up ⁹ Post-neoadjuvant tx
	-28 days	Day of Cycle (± 7 days)		4 (+/- 2) weeks post neoadjuvant tx	
		D1	D15		
REQUIRED ASSESSMENTS					
Medical history	X				
Height	X				
Physical examination	X	X	X		
BP, weight	X	X	X		
ECOG performance status	X	X	X		
Complete metabolic panel	X	X	X		
Calculated creatinine clearance	X	X	X		
Platelets, ANC & Hgb	X	X	X		
CA 19-9	X				
Urine pregnancy ³	X				
AE and concomitant medication assessment	X	X	X	X ¹⁰	
Overall survival					X
Disease progression					X
DISEASE ASSESSMENT					
MRI or CT chest, abdomen, pelvis	X			X ⁵	X ⁴
Surgical resection (if applicable)				X	
TREATMENT					
Neoadjuvant FOLFIRINOX		X	X		
CORRELATIVE STUDIES					
Tissue collection	X ⁶			X	
Blood collection	X ⁶			X	
ASSESSMENTS					
PG-SGA questionnaire	X ⁷			X ⁸	
FAACT questionnaire	X ⁷			X ⁸	

Calendar Footnotes:

¹ Baseline assessments performed within 7 days of Cycle 1 Day 1 do not need to be repeated.

² All patients will have a surgical evaluation visit 4 (+/-2) weeks of completing or discontinuing neoadjuvant chemotherapy as part of their routine care. Information collected during this visit will be used for the EOT visit for this study.

³ Required only for women of child-bearing potential.

⁴ Disease progression will be assessed via radiology report from any MRI or CT scans done during the follow-up period per standard of care.

⁵ Repeat imaging may be performed prior to surgical resection at the treating physician's discretion.

⁶ Whenever possible

⁷ PG-SGA and FAACT assessments not completed at baseline can be completed on C1D1 as long as they are done before treatment begins.

⁸ PG-SGA and FAACT assessments should be completed within 4 (+/-2) weeks of completing or discontinuing neoadjuvant chemotherapy.

⁹ Follow-up for survival and disease progression will be done every 3-6 months years 1-3, every 6 months years 4-5, and every 12 months thereafter.

¹⁰ May be done by telephone in lieu of an in-person visit.

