11.4.3 Tumor markers

Tumor markers alone cannot be used to assess objective tumor response. If markers are initially above the upper normal limit, however, they must normalize for a patient to be considered in complete response.

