12. CORRELATIVE SAMPLE COLLECTION & ASSESSMENT, ANALYSIS

12.1 Tissue Collection

The collection of the pancreatic tumor tissue pre- and post-neoadjuvant treatment is an important part of this trial. The goal of these collections is to generate findings from next generation sequencing (NGS) (see 12.2.1 for more details) to predict the pathological response versus progression. Additionally, future, yet undetermined, research studies will be done on any unused

tissue samples that were collected as part of this study. The outcome and survival data will be correlated with next generation sequencing and other future research.

The tissue will be obtained at the time of diagnosis as a standard of care to establish the diagnosis. If there is additional tissue available from the diagnostic biopsy samples, we plan on requesting them either at the time of biopsy (i.e. fresh tissue sample collection for patients who are already enrolled to this study) or from the Pathology Department (i.e. archival tissue). For patients who have biopsies at institutions outside of IUH, the PI and/or his designee will make requests for any additional tissue from those respective institutions' pathology departments.

After the second cycle of neoadjuvant chemotherapy, additional tumor tissue samples that would otherwise be discarded, will be obtained at the time of surgical resection or biopsy (if applicable). If patients do not proceed to surgery (may occur if the patient refuses surgery, is not eligible for surgery or has progression of disease), then an optional biopsy may be completed at the end of neoadjuvant treatment. All research tissue samples will be stored in the IUSCC Tissue Bank or IU CTSI Specimen Storage Facility.

Please refer to the study laboratory manual for complete instructions regarding tissue collection, processing, transfer and storage.

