12.2 Blood Collection

Blood samples for future, yet undetermined, research studies (in addition to the blood samples taken as part of standard of care) will be collected prior to treatment (i.e. at baseline or C1D1 as long as completed before treatment begins) whenever possible and at the time of surgical evaluation (i.e. 4 weeks [+/-2 weeks] post neoadjuvant chemotherapy). These blood samples will be stored in the IUSCC Tissue Bank or IU CTSI Specimen Storage Facility.

Please refer to the study laboratory manual for complete instructions regarding tissue collection, processing, transfer and storage.

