14. STATISTICAL METHODS

14.1 Sample size analysis and accrual

The pathological complete response with traditional chemotherapy in pancreatic cancer is very low (no reported complete response in neoadjuvant studies). We aim to evaluate the complete response rate and the correlation with outcome. So we assume the pathological complete response in traditional chemotherapy to be 1%. We expect that the pathological complete response after 2 cycles of FOLFIRINOX therapy is about 10%. We plan to enroll 48 patients over a 24 months period. Assuming 90% of patients are evaluable for response, we will have 43 patients evaluable for pathological complete response. Patients will be considered non-evaluable and be replaced with new subjects per analysis datasets section below. With evaluable patients, we have 82% power detect a significant difference from the traditional chemotherapy with a 5% Type I error rate using a two sided one-sample test for proportion.

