- Quality of life measures (from PG-SGA and FAACT) will be summarized with descriptive statistics and compared between baseline and 4 weeks post neo-adjuvant therapy with paired t-tests.

Correlative Outcomes:

- Change of biomarkers (including Ca19-9 and other tissue markers) from baseline to after 2 cycles of therapy will be calculated. Paired t-test will be used to test the change. We will correlate the change of Ca19-9 with patients' pathologic complete response using logistic regression model or overall survival using Cox proportional hazards model as appropriate. Biomarkers will also be correlated with PFS and other response outcomes similarly.
- Differential expression will be performed in R using DESeq2. These files will be downloaded and uploaded to Partek Genomics Suite v6.6 for visualization. Pathway analysis will be performed using Ingenuity Pathway Analysis. CIBERSORT analysis to identify the immune cell make up based on gene expression will also be performed. Selected differentially expressed markers will be correlated with outcomes as describe above.

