15. DATA FORMS AND SUBMISSION SCHEDULE

This study will utilize electronic Case Report Form completion in the OnCore[®] database. A calendar of events and required forms are available in OnCore[®]. The OnCore[®] database is a comprehensive database used by the IUSCC Clinical Trials Office (CTO) and supported by the Indiana Clinical and Translational Sciences Institute (CTSI).

Access to data through OnCore[®] is restricted by user accounts and assigned roles. Once logged into the OnCore[®] system with a user ID and password, OnCore[®] defines roles for each user which limits access to appropriate data. New username and passwords can be obtained by going to the following link: <https://redcap.uits.iu.edu/surveys/?s=sYN36a9U5c>. For further questions regarding your oncore account you can contact the CTO Cancer Center Oncore Support via email at: [contact].

All source documents are to remain in the patient's clinic file. All documents should be kept according to applicable federal guidelines. Clinical trial data in OnCore[®] are periodically monitored by the IU Simon Cancer Center Data Safety Monitoring Committee.

Generally, clinical and correlative data will be electronically captured in OnCore[®]. If procedures on the study calendar are performed for standard of care, at minimum, that data will be captured in the medical record. Select standard of care data will also be captured in OnCore[®], according to study-specific objectives. Please see the OnCore[®] data collection guidelines for further details. Tissues will be stored in the IUSCC and data will be kept in OnCore[®] in a BSM.

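### CA 19-9 is required only at baseline, yet its change to after 2 cycles is analysed; response rates are timed after 4 cycles of a 2-cycle regimen

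*Combined protocol and SAP*

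**What the plan says.** **CA 19-9.** The first correlative objective (section 2.4) is to "Evaluate change in CA 19-9 and other tissue markers before and after treatment and correlate with outcomes". Section 14.3 makes this operational: "Change of biomarkers (including Ca19-9 and other tissue markers) from baseline to after 2 cycles of therapy will be calculated". It tests the change with a paired t-test, then relates the CA 19-9 change to pCR by logistic regression or to overall survival by a Cox model, as appropriate.

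The Study Calendar in section 10 lists CA 19-9 among the required assessments with one mark, in the Baseline column. There is no mark under Cycles 1-2, Surgical Evaluation/EOT or follow-up, and no footnote adds one.

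Section 11.4.3 also depends on a later value: "If markers are initially above the upper normal limit, however, they must normalize for a patient to be considered in complete response".

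Three places come close to supplying a second value, but none orders it:

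- Section 15: "Select standard of care data will also be captured in OnCore[®], according to study-specific objectives".
- Section 10, footnote 2, on the routine surgical evaluation: "Information collected during this visit will be used for the EOT visit for this study".
- Section 12.2: "Blood samples for future, yet undetermined, research studies (in addition to the blood samples taken as part of standard of care) will be collected". This includes a draw at the surgical evaluation, but CA 19-9 is not named.

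**Response time point.** Section 14.3 times objective response rate (ORR) and disease control rate (DCR) after 4 cycles. Section 7.1 gives 2 cycles of 28 days with treatment on days 1 and 15, and section 14.2 counts 4 treatments in all.

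**The concern.** A change score needs two measurements, and the protocol requires one. If the second depends on clinicians' ordering habits, three things follow. The number of pairs is uncontrolled. The timing of the second value is not fixed. The patients who have one may differ from those who do not, for instance if the test is ordered more often when progression is suspected.

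The gap also reaches radiological response. Under section 11.4.3, a patient whose marker was raised at baseline cannot be confirmed as a complete response without a later value. ORR and DCR totals should not move, because both count partial as well as complete responses.

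The tissue markers do not share the problem: section 12.1 plans post-treatment tissue from surgery or biopsy.

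The 4-cycle wording is a separate fault. Read literally, it sets two secondary endpoints at a time that no patient reaches on protocol treatment.

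**Working it through.** **1. The plan's own figure.** Section 14.1 states that "we will have 43 patients evaluable for pathological complete response" and claims 82% power for 1% against 10%, two-sided 5%. Evaluable patients: 48 × 0.90 = 43.2, so 43. An exact binomial test that rejects at 3 or more pCRs of 43 has power 0.818 at 10% and upper-tail error 0.009 at 1%. A cut-off of 2 gives error 0.069, which is too high. The 82% is reproduced, and nothing below alters it.

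**2. Measurements required.** CA 19-9 has one time point in the calendar; a paired change needs two. The other paired t-test in section 14.3, on PG-SGA and FAACT, has both time points marked. Other calendar rows (adverse events, imaging, tissue, blood, questionnaires) also carry post-treatment marks, so the single CA 19-9 mark does not look like a fault in reading the table.

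**3. What the loss could cost.** The document gives no rate of routine post-treatment testing. I assume 50% to 90% of 48 patients: 48 × 0.50 = 24 and 48 × 0.90 = 43.2, so 43 pairs.

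- *Paired t-test*, two-sided 5%, 80% power. The normal approximation to the detectable standardised change is (1.960 + 0.842)/√n. The table uses the noncentral t distribution, which gives slightly larger values.
- *Logistic model*, pCR on standardised CA 19-9 change, with pCR at the plan's 10% and testing unrelated to pCR. SE(log OR per SD) = 1/√(n × 0.1 × 0.9); detectable OR = exp(2.802 × SE).

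| Pairs | Detectable change (SD) | Expected pCRs | SE(log OR) | Detectable OR per SD |
|---|---|---|---|---|
| 48 | 0.413 | 4.8 | 0.481 | 3.85 |
| 43 | 0.437 | 4.3 | 0.508 | 4.15 |
| 24 | 0.597 | 2.4 | 0.680 | 6.73 |

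With so few events the odds ratios are rough. At 90% coverage the loss is small; at 50% it is material for the t-test. The logistic model is weak even with all 48 pairs.

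**4. Cycles.** 2 cycles × 2 treatments = 4 treatments over 8 weeks. Four cycles would be 4 × 2 = 8 treatments over 16 weeks, twice the regimen. Section 14.1 and the biomarker text in section 14.3 both say 2 cycles, so the 4 is most likely a count of treatments labelled as cycles.

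**The case against.** The best reply is that the data may well exist. Post-treatment CA 19-9 may be measured in routine care, and section 15 allows such values to be captured. It also refers to OnCore data collection guidelines that are not in the document and might list the test. Blood is banked at the surgical evaluation, and section 3.4 describes it as stored for further analysis as well as future research, so a missing value might be assayed later. The aim is only correlative, CA 19-9 is not named among the correlative outcome measures, the plan claims no power for it, and the complete response rate alone is not a planned analysis.

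Much of this stands. The loss is not shown to be permanent, its size rests on an assumed coverage, and the stakes are modest. The coverage range can also be questioned: if only the 43 pCR-evaluable patients enter the logistic model, 50% to 90% coverage leaves about 21 to 39 pairs (43 × 0.50 = 21.5; 43 × 0.90 = 38.7), somewhat fewer than shown. Most of that model's weakness comes from the 10% pCR rate, not from the calendar.

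The gap itself remains. Permission to capture a value does not order the test. Banked blood is not assigned to CA 19-9, and its suitability for the assay is not stated.

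On the 4-cycle wording, only one reading is workable, so a careful analyst would reach the right time point. It is still wrong as written.

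**Conclusion.** The concern holds on both counts. The protocol states an objective and an analysis that need a post-treatment CA 19-9, and it requires none. ORR and DCR carry a time point outside the regimen.

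The consequence for CA 19-9 is an analysis on an unknown and possibly selected subset. Under assumed coverage of 50% to 90%, the detectable change is 0.60 to 0.44 SD instead of 0.41 SD. Complete response also cannot be confirmed in patients whose marker was raised at baseline and not repeated. The primary pCR analysis, its power, and the ORR and DCR totals are unaffected. The correction prevents further loss; it does not rescue the logistic model, which would expect only 4.8 events with complete data. The inconsistencies are certain from the text; the extent of missing data is not.

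**What to change.** 1. In the Study Calendar, mark CA 19-9 in the Surgical Evaluation/EOT column, to be run at the blood draw already scheduled there.
2. In section 14.3, time ORR and DCR at the post-neoadjuvant, pre-surgery scan after 2 cycles (4 treatments).
3. As a minor clean-up, reword calendar footnote 5, which makes repeat imaging before surgery discretionary. Section 7.1 directs that scan and section 9.2 relies on it for operative planning.

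The cost is a small amendment: one extra laboratory test per patient at an existing visit, plus the wording changes. It adds no visit or scan and does not alter the sample size. The change helps only patients who have not yet passed the visit. For any others, a value in the chart or an assay of banked blood could be tried, if the sample is suitable.

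### CA 19-9 change is tested with no stated transformation and related to pCR by logistic regression with about 4 expected events and no small-sample method

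*Combined protocol and SAP*

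**What the plan says.** Section 2.4 makes the change in CA 19-9, and its correlation with outcomes, the first correlative objective. Section 14.3 (Correlative Outcomes) computes the change in biomarkers from baseline to after two cycles and states "Paired t-test will be used to test the change". It then relates the CA 19-9 change to "pathologic complete response using logistic regression model", or to overall survival by a Cox model, whichever is appropriate.

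No log, ratio or rank analysis is named. Neither is a penalised or exact logistic fit, a minimum number of pCRs, or a fallback if none occur.

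Section 14.1 fixes the likely number of events. It says "We expect that the pathological complete response after 2 cycles of FOLFIRINOX therapy is about 10" per cent and "we will have 43 patients evaluable for pathological complete response".

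The Section 10 calendar marks CA 19-9 in the baseline column only.

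**The concern.** There are two separate weaknesses. First, a logistic slope fitted by maximum likelihood to about four events is biased away from zero on average, is very imprecise, and cannot be estimated at all if there are no events. Second, if the marker is right-skewed and changes proportionally, a few patients with high values dominate both the mean difference and its variance. A paired t-test on absolute change is then a weak way to show a typical fall. The same change score is also the covariate for pCR and survival.

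What is at stake is a stated correlative objective. A real proportional fall could go undetected, or an exaggerated odds ratio could be carried into the planning of later studies.

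**Working it through.** **Inputs from Section 14.1.** Enrolment is 48 ("We plan to enroll 48 patients over a 24 months period"), with "Assuming 90% of patients are evaluable for response". The expected pCR rate is 10% and the reference rate 1%. The primary test is specified "with a 5% Type I error rate using a two sided one-sample test for proportion".

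**The plan's own figure.** 48 x 0.90 = 43.2, taken as 43. Rejecting at 3 or more pCRs in 43 gives an exact type I error of 0.0092 and power 1 - P(X<=2 | 10%) = 1 - 0.182 = 0.818. The stated 82% reproduces. It belongs to the primary test; the plan states no power for CA 19-9.

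**Event count.**
- Expected pCRs: 43 x 0.10 = 4.3 (48 x 0.10 = 4.8 if all enrolled patients count).
- No pCR at 10%: 0.90^43 = 0.011.
- No pCR at the 1% reference rate: 0.99^43 = 0.649.
- Two or fewer at 10%: 0.182.

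**Logistic slope, by simulation.** n=43, 10% event rate, one standard normal covariate, thousands of datasets per OR. Separated datasets were left out of the ML summaries.

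| True OR per SD | ML, mean log-OR | Firth, mean log-OR | RMSE, ML vs Firth |
|---|---|---|---|
| 1 | no bias | no bias | not tabulated |
| 2 | inflated 20-24% | within about 2% of true | 0.97-1.02 vs 0.64-0.66 |
| 3 | inflated 22-27% | within about 2% of true | 1.13-1.33 vs 0.74-0.77 |

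The ranges are the spread over repeated simulations. The ML mean moves because near-separated datasets give extreme estimates. The ML median is inflated by only about 6-8%. Complete separation occurs in about 1% of datasets with at least one event. At a true OR of 2 the central 95% range of ML estimates is 0.60 to 18.7.

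**Power for the pCR association at OR 2 per SD of log change** (log baseline SD 1-2, log change SD 1.0):
- untransformed change, likelihood-ratio test: 0.09-0.10;
- log change, likelihood-ratio test: 0.28-0.30 (rejection rate at OR 1: 0.058-0.071);
- log change, Firth penalised likelihood-ratio test: 0.23-0.24 (rejection rate at OR 1: 0.041-0.047).

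**Paired test, by simulation.** The documents give no CA 19-9 distribution, so all of the following is assumed: log-normal values, log baseline SD s = 1 to 2, SD of log change d = 0.8 to 1.2, a 40% geometric-mean fall and 43 complete pairs. Two models of change were tried.
- *Model A, change independent of baseline.* The arithmetic mean ratio is 0.6 x exp(d^2/2), which is 0.83, 0.99 and 1.23 at d = 0.8, 1.0 and 1.2.
- *Model B, equal log spread at both visits.* The correlation of the logs is 1 - d^2/(2s^2), and the arithmetic mean ratio stays at 0.6.

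| Setting | Untransformed, A | Untransformed, B | Log scale |
|---|---|---|---|
| s=1, d=0.8 | 0.34 | 0.82 | 0.98 |
| s=2, d=1.2 | 0.03 | 0.17 | 0.78 |
| Range over all settings | 0.03-0.34 | 0.17-0.82 | 0.78-0.98 |

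The log-scale test had the higher power in every setting, but the gap depends heavily on the model of change.

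**Second measurement.** Sections 2.4 and 14.3 need a post-treatment CA 19-9. Section 10 schedules none. Section 12.2 does collect blood at the surgical evaluation, but assigns it to research not yet determined. The 43 complete pairs assumed above are therefore not secured by the schedule.

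**The case against.** The strongest reply is that the plan leaves the scale and the fitting method open and does not choose badly. That is correct. A reader might infer that the plan commits to absolute change and ordinary maximum likelihood, but the text says neither. Log change and penalised fitting would both be compatible with it. What stands is that these choices are unspecified and could be made after the data are seen.

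It can also be said that the most striking power contrast (3-34% against 78-98%) is partly an artefact. Under Model A with d of 1.0 or 1.2, the arithmetic mean is flat or rises, so there is no fall on that scale to miss. The two tests address different means, and part of the contrast reflects that difference in target. Under Model B the contrast narrows, to 0.82 against 0.98 at best. A reader should not conclude that the t-test is nearly powerless in this trial, because no document figure settles the distribution.

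Nor do the figures support saying that the odds ratio will usually be exaggerated, or that the model will usually fail. The median estimate is close to the truth, there is no bias at OR 1, separation is rare, and the 65% chance of no pCR applies only at the 1% reference rate.

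Finally, the analysis is correlative, carries no power claim and drives no decision. That limits its weight but does not remove the point.

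**Conclusion.** The point holds as a modest improvement to a correlative analysis. It rests on three results of different strength.

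- The event count of about 4.3 comes from the plan's figures alone.
- The inflation of the mean log-odds ratio, and an RMSE about one third lower with Firth, follow from that count given one roughly normal covariate and a true OR of 2-3 per SD.
- The advantage of the log scale is conditional on right skew and proportional change. Its direction was the same in every setting tried, but its size varied widely.

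Penalisation does not rescue the pCR question. With power of 0.23-0.24 at OR 2, about four events cannot answer it under any model, so the result is descriptive. The primary pCR test and its 82% power are untouched. The missing post-treatment CA 19-9 in the calendar comes first in practice, because without a second value there is no change to analyse.

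**What to change.** In Section 14.3:

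1. Analyse log CA 19-9. Apply the paired t-test to the log ratio and report a geometric mean ratio with a 95% CI. State how values below the assay limit are handled.
2. Use the log ratio as the covariate in the logistic and Cox models.
3. Fit pCR by Firth-penalised (or exact) logistic regression, with a profile-likelihood CI for the Firth fit. State that no association is estimated if no pCR occurs.
4. Label the pCR association descriptive.

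Reconcile the Section 10 calendar with Sections 2.4 and 14.3, so that the source and timing of the second CA 19-9 value are stated.

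Items 1 to 4 cost SAP wording only and need no extra patients. The downside is that results are read as ratios and not as absolute changes in concentration. Reconciling the calendar may require capturing a post-treatment value that is not now scheduled.

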7. TREATMENT PLAN

7.1 Treatment Dosage and Administration

Patients on this trial will be treated with neoadjuvant FOLFIRINOX for 2 cycles (1 cycle = 28 days). Patients will receive FOLFIRINOX on an outpatient basis on days 1 and 15 of each cycle. Following neoadjuvant treatment, patients will undergo repeat imaging (CT or MRI) to be reassessed for resectability of the tumor. Further adjuvant treatment will be determined at the treating physician's discretion (i.e. chemoradiotherapy or adjuvant chemotherapy). It is important to note that post-neoadjuvant therapy is determined by the treating physician per their institutional guidelines and standard of care. While this study will collect data regarding disease progression and survival from the post-neoadjuvant period, this protocol does not dictate post-neoadjuvant treatment which may be done at other institutions.

For patients with an R1 resection, any chemoradiotherapy will be included in the 24 weeks of perioperative therapy. Chemoradiotherapy and the timing in which it will be given will be determined at the treating physician's discretion based on margin status and the patient's recovery. Furthermore, patients who receive chemoradiotherapy may also receive adjuvant chemotherapy; however, this will be based on the treating physician's discretion. Recommended radiosensitization will be through 5FU 200 mg/m²/Day continuous infusions M-F of each week or capecitabine 825 mg/m² PO BID M-F for the duration of radiation therapy. Patients who

receive adjuvant therapy will receive treatment based upon treating physician's discretion with a recommended duration of therapy lasting 6 months accounting for preoperative therapy.

The neoadjuvant FOLFIRINOX regimen starting doses are: oxaliplatin 85 mg/m², followed by leucovorin 400 mg/m² given simultaneously with irinotecan 180 mg/m², followed by 5FU 400 mg/m² bolus and then 2400 mg/m² (Table 1). Patients require a PORT, PICC or other IV access to allow administration of 5FU via a continuous infusion pump. All agents should be administered within SOC drug administration guidelines. Appropriate dose modifications for each agent are described in Section 9.0. See drug monographs/package inserts for full details on each agent.

Agent	Dose*	Route	Schedule
Oxaliplatin	85 mg/m ² in 250 cc D5W	IV before irinotecan	Day 1,15 of each 28 day cycle

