14.3 Statistical analysis plan

Primary Outcome:

- Pathologic complete response: the proportion of the 48 patients having a pathologic complete response with a 95% confidence interval (using normal approximation) will be calculated.

Secondary Outcomes:

- *Safety:* Adverse events of grades 3, 4, 5 by the CTCAE v4.3 criteria for each category listed in section 2.1.6 will be summarized. The proportion of patients with each category of AE will be calculated with a 95% confidence interval. After the enrollment of the first 20 patients, we will evaluate the rate of surgical resection. If >6 patients are not able to proceed with surgery due to excessive toxicity or progression (not including occult metastatic peritoneal disease that was found during surgery and not on imaging) the study will discontinue due to unacceptable toxicity.

- *Ability of patients to undergo surgical resection after receiving neoadjuvant FOLFIRINOX*: the proportion of patients who are able to go through surgery among those who have resectable tumor will be calculated accompanied with a 95% confidence interval.
- *Rate of resectability* will be evaluated by determining the proportion of patients who are able to undergo surgery with resection of their primary tumor (R0 vs R1) resection. A 95% confidence interval will be constructed for the rate.
- *Disease free survival (DFS)*: DFS is defined as time from registration to evidence of tumor recurrence (including clinical deterioration related to the underlying pancreatic cancer, as assessed by the investigator) or death from any cause. Kaplan-Meier curve for DFS will be plotted. Median DFS time will be calculated accompanied with a 95% confidence interval.
- *Overall survival*: time from registration to death for 48 patients with right censoring will be analyzed using Kaplan-Meier estimate. Median survival time will be obtained accompanied with a 95% confidence interval.
- *Objective response rate*: proportion of patients with complete responses (CR) or partial responses (PR) after 4 cycles of FOLFIRINOX treatment will be constructed with a 95% confidence interval.
- *Disease control rate*: Proportion of patients with complete responses (CR), partial responses (PR), or stable disease (SD) after 4 cycles of FOLFIRINOX treatment will be obtained with a 95% confidence interval.

Tertiary Outcomes:

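### Post-treatment marker change is to be related to PFS, but PFS is undefined, the second CA 19-9 sample is unscheduled and no landmark is set, so progressions already present at that sample could inflate the hazard ratio

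*Combined protocol and SAP*

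**What the plan says.** The covariate is defined in section 14.3, Correlative Outcomes: "Change of biomarkers (including Ca19-9 and other tissue markers) from baseline to after 2 cycles of therapy will be calculated". The change in CA 19-9 is then related to pathologic complete response by logistic regression, or to "overall survival using Cox proportional hazards model as appropriate". The next sentence extends this: "Biomarkers will also be correlated with PFS and other response outcomes similarly". For a time-to-event outcome, that means Cox regression. Selected expression markers are to be handled in the same way.

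The time origins come from the Secondary Outcomes of section 14.3. Overall survival is "time from registration to death for 48 patients with right censoring". For the other endpoint, "DFS is defined as time from registration to evidence of tumor recurrence". PFS has no definition, event list or origin in the plan.

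On timing, section 7.1 gives two 28-day cycles and then says: "Following neoadjuvant treatment, patients will undergo repeat imaging (CT or MRI) to be reassessed for resectability of the tumor". A footnote to the study calendar (section 10) adds: "All patients will have a surgical evaluation visit 4 (+/-2) weeks of completing or discontinuing neoadjuvant chemotherapy". The repeat scan sits in that visit's column, and section 12.2 puts the post-treatment research blood draw at the same visit. The calendar's CA 19-9 row is marked at baseline only.

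The plan states no landmark, delayed entry or time-dependent covariate, and no rule for a patient who progresses before the second marker value.

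**The concern.** The marker change does not exist until about two to three months into the study. If the PFS clock starts earlier, at registration, a patient whose progression shows at or before the second sample enters the model with an event that precedes or coincides with the covariate. A raised marker in that patient records the progression and does not predict it. The Cox model cannot tell the difference, so the hazard ratio moves away from 1.

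The plan expects such patients. Sections 9.1 and 12.1 name progression as a reason for not reaching surgery and allow a biopsy at the end of treatment in those patients. The 20-patient rule in section 14.3 counts them.

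What is at stake is correlative objective 1 (section 2.4). In a trial of this size, a marker could be carried forward because it registered progression that had already happened.

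**Working it through.** **The plan's own figure.** The biomarker analysis has none. The only design figure is the 82% power in section 14.1. It reproduces: with 43 evaluable patients and rejection at 3 or more complete responses, exact binomial power at 10% is 81.8%, and the one-tail error at 1% is 0.9%. It does not bear on this point.

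**Timing.** Cycle 2 day 15 is 28 + 14 = 42 days (6 weeks) after cycle 1 day 1; cycle 2 ends at 2 × 28 = 56 days (8 weeks). A visit 4 ± 2 weeks after the last dose falls at weeks 8-12; counted from the end of cycle 2, it falls at weeks 10-14. So the scan and research blood draw fall at roughly weeks 8-14. A draw specified only as after two cycles could come before, with or after the scan.

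**Inputs.**
- n = 43 (section 14.1: 48 × 0.90 = 43.2).
- Share progressing before the sample, q: assumed 5-20%. Section 1.3 reports 3 of 21 (14%) progressing on FOLFIRINOX, but in borderline resectable and locally advanced disease.
- Marker shift in those patients, s: assumed 0-1.5 SD; no source in the documents.
- True hazard ratio after the sample: 1.00 per SD.

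**Hand calculation.** Under the null, the Cox score sums (marker of the patient with the event − mean marker of those at risk). Later events contribute zero on average. With m early progressors, the k-th early event contributes s(n − m)/(n − k + 1). For m = 6 (6/43 = 14%) and s = 1:

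37 × (1/43 + 1/42 + 1/41 + 1/40 + 1/39 + 1/38) = 37 × 0.1484 = 5.49

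Assume a median PFS of 12 months after the sample and 36 months of follow-up from it. Later events number 37 × (1 − 2^(−36/12)) = 37 × 0.875 = 32.4, giving about 38.4 events in all. With information of about 1 per event, log HR ≈ 5.49/38.4 = 0.143, so HR ≈ 1.15. Then z ≈ 5.49/√38.4 = 0.89, and the rejection rate is about Φ(0.89 − 1.96) + Φ(−0.89 − 1.96) ≈ 14%.

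**Simulation.** Sample at 3 months, median PFS 12 months after it, censoring at 36 months, 600 replicates per setting:

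| q | From registration, s = 1: mean HR (false positives) | From registration, s = 1.5: mean HR (false positives) | Landmark, s = 1: mean HR (false positives) |
|---|---|---|---|
| 5% | 1.07 (8%) | 1.10 (about 10%) | 1.01 (6%) |
| 10% | 1.13 (12%) | 1.19 (about 22%) | 1.00 (5%) |
| 15% | 1.19 (18%) | 1.31 (35%) | 1.00 (6%) |
| 20% | 1.26 (29%) | 1.38 (46%) | 1.02 (7%) |

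At q = 0 or s = 0 the hazard ratio is about 1.00 and the false-positive rate is near 5%.

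A separate simulation used other assumptions: sample at 2.8 months ± 2 weeks, median 14 months after it, censoring uniform over 12-36 months, 3,000 trials per setting. It gives 19% false positives (median HR 1.21) at q = 14%, s = 1, and 30% at q = 20%, s = 1. Its landmark analysis stays near 5%.

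**Overall survival.** A progression is not a death, and a patient who dies before the sample has no change value and leaves the model. Moving every clock by the same amount leaves the risk sets unchanged, so the hazard ratio changes by exactly 0. With ± 2 weeks of variation in sample date, the largest change in log HR in any replicate was 0.03.

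**The case against.** The strongest reply is that the mechanism needs two facts the documents do not supply.

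First, the origin of PFS. Section 7.1 speaks of collecting progression and survival data from the post-neoadjuvant period, and the calendar lists disease progression only under long-term follow-up. A post-treatment origin is compatible with that.

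Second, the order of events. No scan is scheduled during the two cycles, so a draw soon after cycle 2 would precede most scan-detected progressions, which would then be genuine later events. Patients who stop early for progression may have no second value at all.

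Both points stand, and they make the bias conditional. They do not remove it: nothing in the plan secures the harmless order, and the research blood draw and repeat scan are already set for the same visit.

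The size is also assumption-driven. The 14% comes from more advanced disease than this trial enrols, and the marker shift is not sourced. That stands too.

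Three stronger readings are tempting, and the documents do not support them. A reader might infer that the overall survival model is biased in the same way; it is not, for the reasons shown above. What remains for OS is selection: the result applies to patients who survive to the sample. A reader might also extend the point to DFS. However, section 14.3 does not name DFS in the marker sentences, and section 3.2 lists it for resected patients, which leaves out those whose progression prevents surgery. Finally, a reader might conclude that the plan would report CA 19-9 change as prognostic whatever the truth. Yet in the separate simulation at 14% early progression, even a shift of 1.5 SD gives 34% false positives, so about two thirds of such trials would not reject. The plan says correlate, not predict.

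**Conclusion.** The point holds for PFS, conditionally. Three gaps are firm: PFS is undefined, the second CA 19-9 sample is not in the calendar, and no landmark is stated for a covariate known only after treatment. If PFS runs from registration and the sample falls around the post-treatment scan, the bias is real. With 5-20% early progression and a 1 SD marker rise, the spurious hazard ratio is about 1.07-1.26 per SD, with false positives at about 8-30%. Those figures rest on the assumed early-progression rate, marker shift, event medians and censoring.

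This is a minor point. The analysis is exploratory, and the primary endpoint, sample size and stopping rule do not depend on it.

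**What to change.** Three short additions:

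1. In section 14.3, define PFS: its events, its time origin and its censoring rule.
2. In the study calendar, schedule the post-treatment CA 19-9 sample with a window, and state its place relative to the repeat scan.
3. In section 14.3, state that models using post-treatment marker change start the clock at that sample (a landmark). For PFS, include patients alive and progression-free at that date; apply the same rule to DFS if it is modelled this way. For OS, require only that the patient is alive; dropping living patients who have progressed would discard valid information. Report the number excluded from each model.

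The same rule should cover any expression marker measured after treatment.

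The cost is a few sentences, one calendar entry and the loss of a few patients from an exploratory model. At 5-20% early progression, that is about 2 to 9 of 43 (43 × 0.05 = 2.2; 43 × 0.20 = 8.6) for PFS. The result then applies only to patients event-free at the landmark, and the report should say so.
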